#### **5.2.2.2 Asthma Control Questionnaire (ACQ-6)**

The ACQ-6 is a shortened version of the ACQ that assesses asthma symptoms (night-time waking, symptoms on waking, activity limitation, shortness of breath, wheezing, and short-acting  $\beta_2$ -agonist use) omitting the FEV1 measurement from the original ACQ score.

Subjects will be asked to recall how their asthma has been during the previous week by responding to 1 question regarding their BD use, and 5 questions pertaining to their asthma symptoms.

Questions are weighted equally and scored from 0 (totally controlled) to 6 (severely uncontrolled). The mean ACQ-6 score is the mean of the responses. Mean scores of  $\leq 0.75$  indicate well-controlled asthma, scores between 0.75 and  $\leq 1.5$  indicate partly controlled asthma, and a score  $>1.5$  indicates uncontrolled asthma (Juniper et al 2006). Individual changes of at least 0.5 are considered to be clinically meaningful.

The questionnaire will be completed using the ePRO device.

Visit 1 ACQ-6 scores will determine eligibility for run-in and randomization (see section 3.1 inclusion criterion 11). An initial screening ACQ-6 will be taken at Visit 1 at study site. At Visit 3 subjects will complete ACQ-6. Once randomized, subjects will be asked to complete ACQ-6 once every 2 weeks ( $\pm 1$  day) throughout the treatment period.

The Investigator/authorized delegate will check subject’s adherence to the ACQ-6 at each visit as shown in Table 1.

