#### **5.2.2.3 Standardised Asthma Quality of Life Questionnaire for 12 Years and Older (AQLQ(S)+12)**

The AQLQ(S)+12 is a questionnaire that measures the health related quality of health-related quality of life assessment questionnaire developed for asthma subjects ages 12 and above.

The questionnaire comprises 4 separate domains (i.e., asthma symptoms, activity limitations, emotional function, and environmental stimuli).

Subjects will be asked to recall their experiences during the previous 2 weeks and to score each of the questions on a 7-point scale ranging from 7 (no impairment) to 1 (severe impairment). The overall score will be calculated as the mean response to all questions. The 4 individual domain scores (symptoms, activity limitations, emotional function, and environmental stimuli) are the means of the responses to the questions in each of the domains. Individual improvement in both the overall score and individual domain scores of 0.5 has been identified as a minimally important change. The questionnaire will be completed using the subject's ePRO device.

The AQLQ(S)+12 will be first completed by the subject at the site at Visit 3 (Week 0), then every 4 weeks ( $\pm 1$  day) throughout the treatment period. At the EOT visit the AQLQ(S)+12 will be completed during the visit unless completed the day prior.

The Investigator/authorized delegate will check the subject's adherence to AQLQ(S)+12 at each visit as shown in [Table 1](#).

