#### **8.4.3.1 Asthma symptom score**

Asthma symptoms during night-time and daytime will be recorded by the subject each morning and evening in the Asthma Daily Diary. Symptoms will be recorded using a scale 0-3, where 0 indicates no asthma symptoms. Asthma symptom daytime score, night-time score, and total score will be calculated separately.

The total daily symptom score will be calculated by taking the sum of the daytime and night-time asthma symptom scores for each day. If a subject is missing a value for either daytime or night-time asthma symptom score on a given day then the total score for that day will be set to missing.

The key secondary outcome variable is the biweekly mean daily asthma symptom total score. The daily asthma symptom total score is defined as the sum of the daytime and night-time symptom scores as captured in the Asthma Daily Diary. The biweekly mean is calculated as the mean daily asthma symptom total over 14 sequential days. If more than 7 daily scores (>50%) within that period is missing, then the daily asthma symptom mean score is set to 'missing'.

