### 8.5.1 Testing strategy for primary and key secondary objectives

The pre-defined hierarchical testing strategy for testing of the primary and key secondary hypothesis in the primary populations described below, gives global strong control of the Type I error (FWER).

**Step 1:** The primary endpoint in the biomarker positive population will be tested two-sided at  $\alpha=0.05$

**Step 2:** If a significant treatment effect is shown with regards to the primary endpoint in the biomarker positive population in Step 1, then the key secondary endpoint, percent change from baseline in pre-dose/pre-BD FEV1 at Week 52 vs. placebo will be tested two-sided at  $\alpha=0.05$  within that population using the hierarchical testing approach. Otherwise, testing will stop. All subsequent results within the hierarchy will be declared non-significant.

**Step 3:** If a significant treatment effect is shown with regards to the key secondary endpoint percent change from baseline in pre-dose/pre-BD FEV1 at Week 52 vs. placebo in the biomarker positive population in Step 2, then the next key secondary endpoint, change from baseline in AQLQ(S)+12 at Week 52 vs. placebo will be tested two-sided at  $\alpha=0.05$  within that population using the hierarchical testing approach. Otherwise, testing will stop. All subsequent results within the hierarchy will be declared non-significant.

**Step 4:** If a significant treatment effect is shown with regards to the key secondary endpoint change from baseline in AQLQ(S)+12 at Week 52 vs. placebo in the biomarker positive population in Step 3, then the next key secondary endpoint, change from baseline in ACQ-6 at Week 52 vs. placebo will be tested two-sided at  $\alpha=0.05$  within that population using the hierarchical testing approach. Otherwise, testing will stop. All subsequent results within the hierarchy will be declared non-significant.

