**Step 5:** If a significant treatment effect is shown with regards to the key secondary endpoint of change from baseline in ACQ-6 at Week 52 vs placebo in the biomarker positive population, then the key secondary endpoint of change from baseline in bi-weekly mean daily asthma symptom score at Week 52 vs placebo in the biomarker positive population and the primary endpoint in the all subjects population will be tested using a Bonferroni approach at significance  $\alpha$ . Hence, each of the two endpoints will be tested at significance level  $\alpha/2$  ( $=0.025$ ). If at least one significant treatment effect is shown at this step, testing will continue

to step 6. Otherwise, testing will stop. All subsequent results within the hierarchy will be declared non-significant.

**Step 6:** Percent change from baseline in pre-dose/pre-BD FEV1 at Week 52 vs. placebo in the all subjects population will only be tested if at least one significant treatment effect is shown at step 5. There are two different outcomes in Step 5 that could result in testing the hypothesis for FEV1:

- (a) If both comparisons in step 5 exhibits significance, then FEV1 in the all subjects population is testable and will be tested at significance level  $\alpha$  ( $=0.05$ ).
- (b) If only one of the hypotheses in step 5 exhibits significance, then FEV1 in the all subjects population is testable and will be tested at significant level  $\alpha/2$  ( $=0.025$ ).

**Step 7:** If a significant treatment effect is shown with regards to percent change from baseline in pre-dose/pre-BD FEV1 at Week 52 vs. placebo in the all subjects population then change from baseline in AQLQ(S)+12 at Week 52 vs placebo will be tested using the significance level used in step 6 ( $\alpha$  ( $=0.05$ ) if outcome (a) from Step 5, or  $\alpha/2$  ( $=0.025$ ) if outcome (b) from step 5). Otherwise, testing will stop. All subsequent results within the hierarchy will be declared non-significant.

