#### 8.5.7.1 Lung Function

**The key secondary outcome variable for lung function is:** Percent change from baseline in pre-dose/pre BD FEV1.

The percent change from baseline in pre-dose/pre-BD FEV1 at Week 52 will be compared between tralokinumab and placebo using a repeated measures analysis on all subjects with a baseline pre-dose/pre-BD FEV1 measurement in the full analysis set.

The dependent variable will be the percent change from baseline in pre-BD FEV1 at post-baseline protocol-specified visits (up to the EOT visit). Treatment group and the variables used in the stratified randomization will be included as independent variables. Visit will be fitted as a categorical variable, and the variance-covariance matrix will be assumed to be unstructured. If the procedure does not converge then a compound symmetric variance-covariance matrix will be used instead. The model is:

$$\text{Percent change in FEV1} = \text{Treatment group} + \text{stratifying variables} + \text{visit} + \text{treatment} * \text{visit}$$

Results will be presented in terms of LSMEANS, treatment differences in LSMEANS, 95% confidence intervals and p-values. Summary statistics of the change from baseline for all visits in the FEV1 at study site will be produced by treatment group.

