#### 8.5.7.2 Asthma symptoms

**The key secondary outcome variable:** Change from baseline in bi-weekly mean daily asthma symptom score (combined daytime and night-time score as captured in the Asthma Daily).

The change from baseline in asthma symptom total score, daytime score, and night-time score at Week 52 will each be summarized and analyzed using the repeated measurement approach defined for change from baseline in pre-dose/pre-BD FEV1, as described in Section 8.4.2.4. Included in the model will also be the baseline mean daily asthma symptom score.

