#### 8.5.7.4 ACQ-6 defined asthma control

**The key outcome variable:** Change from baseline in ACQ-6.

Change in mean score from baseline for ACQ-6 will be summarized and analyzed using the repeated measurement approach defined for change from baseline in pre-dose/pre-BD FEV1, as described in Section 8.4.2.4. Included in the model will also be the baseline ACQ-6 mean score.

**Supportive outcome variable:** ACQ-6 responder (yes/no).

Responder variables ACQ-6 (yes/no) will be analyzed using a logistic regression model with covariates of at least treatment, stratifying variables, and baseline value.

The number and percentage of subjects achieving mean ACQ-6  $\leq 0.75$ ,  $0.75 < \text{mean ACQ-6} < 1.5$  and mean ACQ-6 of  $\geq 1.5$  at EOT will be summarized by treatment. Additionally, the number and percentage of subjects achieving an improvement, no change, or deterioration as per Section 8.4.3.4, ACQ-6 will also be summarized by treatment.

**Supportive outcome measure:** change from baseline to overall post-baseline mean of ACQ-6.

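### If the unstructured model fails to converge, the one-step fallback to compound symmetry can make the Week 52 standard error for ACQ-6 and symptom score too small

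*Protocol*

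**What the plan says.** Section 8.5.7.1 sets out the model for percent change in pre-BD FEV1: treatment, stratifying variables, visit as a category, treatment by visit, and an unstructured covariance matrix. It then adds: "If the procedure does not converge then a compound symmetric variance-covariance matrix will be used instead". It names no intermediate structure, no heterogeneous-variance version and no empirical standard error.

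The rule carries over to the other key secondary endpoints, each with its baseline score added to the model. Symptom score is "analyzed using the repeated measurement approach defined for change from baseline in pre-dose/pre-BD" FEV1 (Section 8.5.7.2). For ACQ-6, "Change in mean score from baseline for ACQ-6 will be summarized and analyzed using the repeated measurement approach" (Section 8.5.7.4). Section 8.5.7.3 treats AQLQ(S)+12 alike. All three point to Section 8.4.2.4, which only derives the FEV1 variable; the model is in 8.5.7.1.

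These are confirmatory tests in the biomarker-positive population (Section 8.5.1). In Step 4, "change from baseline in ACQ-6 at Week 52 vs. placebo will be tested two-sided" at 0.05. In Step 5, symptom score is paired with the primary endpoint in all subjects, and "each of the two endpoints will be tested at significance level" 0.025. The section claims strong familywise error control.

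On the number of time points, "subjects will be asked to complete ACQ-6 once every 2 weeks" (Section 5.2.2.2). Symptom score is a mean over 14 days (Section 8.4.3.1). AQLQ(S)+12 is completed at Week 0 and "then every 4 weeks" (Section 5.2.2.3).

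**The concern.** The fallback goes straight from the most flexible structure to one with equal variance at every visit and equal correlation at every gap. The tested contrast is the treatment difference at Week 52 only. Under compound symmetry its model-based standard error uses a variance averaged over all visits. If Week 52 is more variable than that average, the standard error is too small and the test exceeds its level.

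A rise in residual variance needs no change in the disease. Baseline is a covariate, so residual variance is proportional to 1 − ρ², where ρ is the correlation with baseline. If that correlation weakens over a year, residual variance rises even with constant raw variance.

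What is at stake is the nominal level of Step 4 and of the symptom-score half of Step 5. Both are reached only if Steps 1 to 3 all reject.

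**Working it through.** **The plan's own figure.** The protocol gives no SD, correlation or power for these endpoints. Its power figures concern the primary endpoint, and they confirm the population sizes used here. Var(log RR) = [1/r₀ + 1/(r₀·RR) + 2k]/T, with r₀ = 0.8, k = 0.95 and T = 355 subject-years per arm × biomarker-positive share (Section 8.2).
- 50% reduction, 5% level, 20% share: (1.25 + 2.5 + 1.9)/71 = 0.0796, SE 0.282, power Φ(0.693/0.282 − 1.960) = 69.0%. A 35% share gives 90.2%. Stated: 70% to 90%.
- 37% reduction, all subjects, 1% level: 89.7%. Stated: at least 90%.

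**Inputs.**
- Biomarker-positive subjects: 0.20 × 770 = 154 to 0.35 × 770 ≈ 270; 1:1 allocation; 15% uniform dropout (Sections 3.3 and 8.2).
- ACQ-6 and symptom score: 26 two-weekly points, so 26 × 27/2 = 351 covariance parameters. AQLQ(S)+12: 13 points, 13 × 14/2 = 91. The 26 is inferred from the schedule, because Section 8.4.1.2 leaves detailed windows to the SAP.
- Assumed: variances, correlations and intermittent missingness.

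**Mechanism, complete data.** Model SE / true SE = √(mean variance over visits / Week 52 variance). Two-sided error = 2[1 − Φ(z × ratio)]. Example: SD rising linearly 1.25-fold gives mean variance 1 + 0.25 + 0.0625 × 0.34 = 1.271 and Week 52 variance 1.5625, so the ratio is 0.902.

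| SD Week 52 / Week 2, linear | SE ratio | Error at 5% | Error at 2.5% |
|---|---|---|---|
| 0.8 | 1.127 | 2.7% | 1.2% |
| 1.0 | 1.000 | 5.0% | 2.5% |
| 1.1 | 0.955 | 6.1% | 3.2% |
| 1.25 | 0.902 | 7.7% | 4.3% |
| 1.5 | 0.839 | 10.0% | 6.0% |

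If the SD rises early and then levels off, 1.25-fold gives 6.1% and 3.2%, and 1.5-fold gives 7.0% and 3.8%.

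**Simulation.** 6,000 null trials per setting (Monte Carlo SE about 0.3 points at 5%, 0.2 at 2.5%); n = 154, 26 points, 15% dropout; arm by visit plus baseline, strata omitted; compound symmetry by REML; t with n − 3 df. Correlation at a lag in weeks is 0.4 + 0.4·exp(−lag/τ). For τ = 12, ρ with baseline falls from 0.739 (Week 2) to 0.405 (Week 52), so residual SD rises √(0.836/0.454) = 1.36-fold.

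| Setting | Residual SD ratio | SE ratio | Error at 5% / 2.5% |
|---|---|---|---|
| τ = 10 | 1.33 | 0.932 | 6.3 / 3.5 |
| τ = 12 | 1.36 | 0.930 | 6.7 / 3.6 |
| τ = 20 | 1.39 | 0.906 | 7.1 / 4.0 |
| τ = 40 | 1.38 | 0.877 | 8.7 / 4.8 |
| τ = 12, 20% intermittent missingness | – | 0.926 | 6.9 / 3.6 |
| Linear SD rise of 10% | 1.10 | 0.932 | 6.6 / 3.9 |
| Constant variance | 1.00 | 0.972 | 5.7 / 2.8 |
| SD falling 20% | 0.80 | 1.122 | 2.7 / 1.1 |

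The relative error does not depend on sample size: corrected sandwich SE over compound-symmetric SE is 1.079 at n = 154 and 1.076 at n = 270. With 13 points (τ = 12) error is 6.5 / 3.2. Separately coded simulations agree: τ = 12 with 20% missingness gave SE ratio 0.91 and error 7.3 / 4.1; τ = 40 with 20% missingness gave 0.87 and 8.7 / 5.1.

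**How likely is the trigger?** Unstructured REML fits, τ = 12, 15% dropout plus intermittent missingness; fits that converged:
- n = 154, 26 points: 12/12 at each of 0, 10 and 15% missing; 7/14 at 20%; 0/12 at 30%.
- n = 200: 10/10 at 20%; 0/10 at 30%.
- n = 270: 8/8 at 20%; 6/6 at 30%.
- n = 154, 13 points: 24/24 at 20–30%.

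These are small runs. A different algorithm (REML by EM, n = 154, 26 points) reached an interior maximum in 3/8 at 20% and 0/8 at 30%, so the failures are not an artefact of one fitting method.

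**Unconditional error**, for an assumed fallback probability p of 5–20%: nominal + p × excess.
- At 5%: 5 + 0.05 × 1.3 = 5.1% to 5 + 0.20 × 3.7 = 5.7%.
- At 2.5%: 2.5 + 0.05 × 1.0 = 2.6% to 2.5 + 0.20 × 2.3 = 3.0%.

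**The case against.** The trigger is remote. It needs at least 20% intermittent missingness on top of dropout and a biomarker-positive share towards the low end of the planned range. The protocol works against that. Inclusion criterion 19 demands diary compliance before randomization. Section 4.2 has ePRO adherence assessed at every treatment visit, with retraining. A two-week symptom mean is lost only under the rule "If more than 7 daily scores (>50%) within that period is missing". If the SAP analysed four-weekly periods, the demonstrated trigger would disappear. All of this stands and is why the point is minor.

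The text says neither that the compound symmetry is homogeneous nor that the standard error is model-based, and the SAP could add a sandwich variance. True, but equal variance is the ordinary meaning of the term. The one-step fallback is fixed in the protocol, so an SAP naming other structures would contradict it.

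Direction and size are assumed. That also stands: falling variance makes the test conservative, and no single error figure can be attributed to this trial.

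The upper unconditional figure pairs τ = 40 with convergence runs made at τ = 12. Matching τ = 12 with 20% missingness gives 5 + 0.2 × 1.9 = 5.4% and 2.5 + 0.2 × 1.1 = 2.7%. Since τ = 40 with 20% missingness also gave 8.7% in a separate simulation, 5.7% remains a fair upper end for the assumed probability.

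Finally, with Step 1 power near 70% at n = 154, and treating the tests as independent, even a certain fallback gives at most 0.70 × 6.9% = 4.8% false rejection at Step 4. This limits practical harm under the planning effect. Strong control must also hold for larger effects and correlated tests. The sensitivity analyses in Section 8.5.2 do not change the test used in the hierarchy.

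**Conclusion.** The concern holds, as a minor point. If the fallback is used for ACQ-6 or symptom score in about 154 biomarker-positive subjects, and residual SD rises by about a third or somewhat more, the Week 52 standard error is 7–12% too small. The true level is then 6.3–8.7% at Step 4 and 3.5–4.8% for the symptom-score test in Step 5. Averaged over an assumed 5–20% chance of using the fallback, the figures are about 5.1–5.7% and 2.6–3.0%.

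The conclusion rests on 26 modelled time points, the equal-variance reading of compound symmetry, a model-based standard error, and assumed correlations and missingness. Confidence in the size is moderate. Step 1 uses a negative binomial model and is unaffected. AQLQ(S)+12, with 13 points, showed no convergence problem.

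**What to change.** Replace the fallback sentence in Section 8.5.7.1 with:

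> If the unstructured model does not converge, heterogeneous Toeplitz, then heterogeneous AR(1), then heterogeneous compound symmetry will be tried, and the first that converges will be used. Whenever the structure is not unstructured, an empirical (sandwich) variance with small-sample correction will be used.

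Put the same text in the SAP before unblinding, which Section 8.1 allows, and change the protocol sentence so that the two agree. In the same edit, redirect the references to Section 8.4.2.4 in Sections 8.5.7.2 to 8.5.7.4 to Section 8.5.7.1.

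The correction matters. On the compound-symmetric fit, the Mancl-DeRouen-corrected sandwich gave 4.4–5.5% at nominal 5% and 2.1–2.8% at nominal 2.5% in all settings; the uncorrected version gave 5.1–5.8% at nominal 5% in the rising-variance runs at n = 154. The ladder with the corrected sandwich (τ = 12, n = 154, 20% intermittent missingness, 2,500 trials) gave 5.5 / 3.1 for heterogeneous Toeplitz, 5.3 / 2.9 for AR(1) and 5.2 / 2.7 for compound symmetry. Those ladder fits were by moments, not REML, and show no advantage of one rung over another; most of the protection comes from the corrected variance.

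The cost is two sentences and minor programming. Compared with compound symmetry, Week 52 intervals would be about 6–14% wider if variance rises, 2–3% wider if it is constant, and 9% narrower if it falls.

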#### 8.5.7.2 Asthma symptoms

**The key secondary outcome variable:** Change from baseline in bi-weekly mean daily asthma symptom score (combined daytime and night-time score as captured in the Asthma Daily).

The change from baseline in asthma symptom total score, daytime score, and night-time score at Week 52 will each be summarized and analyzed using the repeated measurement approach defined for change from baseline in pre-dose/pre-BD FEV1, as described in Section 8.4.2.4. Included in the model will also be the baseline mean daily asthma symptom score.

#### 8.5.7.3 Asthma specific health-related quality of life

**The key secondary outcome variable:** Change from baseline in AQLQ(s)+12 total score.

The change in mean score from baseline for AQLQ(S)+12 at Week 52 will be summarized and analyzed using the repeated measurement approach defined for change from baseline in pre-dose/pre-BD FEV1, as described in Section 8.4.2.4. Included in the model will also be the baseline AQLQ(s)+12 total score.

**Supportive outcome variable:** AQLQ(S)+12 responder (yes/no)

Responder variables AQLQ(S)+12 (yes/no) will be analyzed using a logistic regression model with covariates of at least treatment, stratifying variables, and baseline value.

The number and percentage of subjects with AQLQ(s)+12 total score changes  $\geq 0.5$  will be summarized by treatment (identified as a large meaningful change). Additionally, the number and percentage of subjects achieving an improvement, no change, or deterioration will be summarized by treatment as per Section 8.4.3.5.

**Supportive outcome measure:** change from baseline to overall post-baseline mean of AQLQ(S)+12.

#### 8.5.7.4 ACQ-6 defined asthma control

**The key outcome variable:** Change from baseline in ACQ-6.

Change in mean score from baseline for ACQ-6 will be summarized and analyzed using the repeated measurement approach defined for change from baseline in pre-dose/pre-BD FEV1, as described in Section 8.4.2.4. Included in the model will also be the baseline ACQ-6 mean score.

**Supportive outcome variable:** ACQ-6 responder (yes/no).

Responder variables ACQ-6 (yes/no) will be analyzed using a logistic regression model with covariates of at least treatment, stratifying variables, and baseline value.

The number and percentage of subjects achieving mean ACQ-6  $\leq 0.75$ ,  $0.75 < \text{mean ACQ-6} < 1.5$  and mean ACQ-6 of  $\geq 1.5$  at EOT will be summarized by treatment. Additionally, the number and percentage of subjects achieving an improvement, no change, or deterioration as per Section 8.4.3.4, ACQ-6 will also be summarized by treatment.

**Supportive outcome measure:** change from baseline to overall post-baseline mean of ACQ-6.

